**Source and Pharmacology:**

An orally or intravenously administered alkylating agent, a second generation imidazotetrazine. A prodrug of MTIC, temozolomide spontaneously decomposes to MTIC at physiologic pH. The cytotoxic effects of MTIC are manifested through alkylation (methylation) of DNA at the O, N guanine positions which lead to DNA double strand breaks and apoptosis. Temozolomide is noncell cycle specific.

Temozolomide is rapidly and completely absorbed after oral administration with a peak plasma concentration (Cmax) achieved in a median Tmax of 1 hour. Food reduces the rate and extent of temozolomide absorption. Mean peak plasma concentration and AUC decreased by 32% and 9%, respectively, and median Tmax increased by 2-fold (from 1-2.25 hours) when temozolomide was administered after a modified high-fat breakfast. A pharmacokinetic study comparing oral and intravenous temozolomide in patients with primary CNS malignancies showed that at 150 mg/m^2 dose temozolomide IV and oral capsules are bioequivalent with respect to both Cmax and AUC of temozolomide and MTIC. Temozolomide has a mean apparent volume of distribution of 0.4 L/kg (%CV=13%). It is weakly bound to human plasma proteins; the mean percent bound of drug-related total radioactivity is 15%. Temozolomide is spontaneously hydrolyzed at physiologic pH to the active species, MTIC and to temozolomide acid metabolite. Cytochrome P450 enzymes play only a minor role in the metabolism of temozolomide and MTIC. About 38% of the administered temozolomide total radioactive dose is recovered in the urine. Overall

clearance of temozolomide is about 5.5 L/hr/m^2. Temozolomide is rapidly eliminated, with a mean elimination half-life of 1.8 hours, and exhibits linear kinetics over the therapeutic dosing range of 75 to 250 mg/m^2/day. A population analysis did not demonstrate any influence of coadministered dexamethasone, prochlorperazine, phenytoin, carbamazepine, ondansetron, H2 receptor antagonists, or phenobarbital on the clearance of orally administered temozolomide.

**The table below lists the anticipated toxicity profile of temozolomide (oral):**

Incidence	Toxicities
Common (>20% of patients)	Constipation, nausea, vomiting, anorexia, alopecia, headache, seizure, fatigue
Occasional (4-20% of patients)	Peripheral edema, skin rash, pruritus, xeroderma, erythema of skin, diarrhea, dysphagia, dizziness, ataxia, hemiparesis, asthenia, fever, stomatitis, abdominal pain, dysgeusia, weight gain, platelet count decreased, white blood cell count decreased, lymphocyte count decreased, urinary incontinence or frequency, cough, dyspnea, infection, anxiety, depression, insomnia, gait disturbance, amnesia, paresthesia, drowsiness, visual disturbances, back pain, arthralgia/myalgia
Rare (≤ 3% of patients)	Stevens-Johnson syndrome, toxic epidermal necrolysis, erythema multiforme, hyperbilirubinemia, transaminitis, injection site reaction (IV formulation), interstitial pneumonitis, pancytopenia (may be prolonged), myelodysplastic syndrome, leukemia secondary to oncology chemotherapy, infections and infestations – other: Pneumocystis pneumonia, pulmonary fibrosis, anaphylaxis, allergic reaction, hepatotoxicity, cholestasis, anemia, aplastic anemia
Pregnancy & Lactation	Pregnancy Category D Adequate, well-controlled studies have not been conducted in humans. Women of childbearing potential should be advised against becoming pregnant while taking temozolomide and for at least 6 months following the end of therapy. Temozolomide administration to rats and rabbits at 3/8 and 3/4 the human dose resulted in the development of malformations of the external organs, soft tissues, and skeleton. These animal studies also demonstrated embryoletality (increased resorptions) at similar doses. There is no information available regarding the transmission of temozolomide during lactation; women should avoid breastfeeding while receiving temozolomide.

**Formulation and Stability:**

Temozolomide capsules are available in six different strengths (5, 20, 100, 140, 180, 250 mg). The capsules vary in size, color, and imprint according to strength. In the US, capsules are packaged in 5-count and 14-count bottles. In other countries temozolomide may be packaged in 5-count, 14-count or 20-count bottles. Temozolomide capsules are stored at 25 °C (77 °F); excursions permitted to 15 °C to 30 °C (59 °F to 86 °F).

**Guidelines for Administration:**

See Treatment and Dose Modifications sections of the protocol.

There is a potential for medication errors involving temozolomide capsules resulting in drug overdoses, which may have been caused by dispensing/taking the wrong number of capsules per day and/or product usage exceeding the prescribed dosing schedule.

When dispensing, it is extremely important that prescribing and dispensing include clear instructions on which capsules, and how many of each capsule(s) are to be taken per day.

Only dispense what is needed for the course, and clearly indicate how many days of dosing the patient will have and how many days are without temozolomide dosing. When counseling patients, it is important for each patient/parent to understand the number of capsules per day and the number of days that they take temozolomide. It is also important for the patient/parent to understand the number of days that they will be off the medication.

Each strength of temozolomide must be dispensed in a separate vial or in its original container (e.g., bottle or sachet). Based on the dose prescribed, determine the number of each strength of temozolomide capsules needed for the full course as prescribed by the physician. For example, 275 mg/day for 5 days would be dispensed as five 250 mg capsules, five 20 mg capsules, and five 5 mg capsules. Label each container with the appropriate number of capsules to be taken each day. Dispense to the patient/parent, making sure each container lists the strength (mg) per capsule and that he or she understands to take the appropriate number of capsules of temozolomide from each bottle or vial to equal the total daily dose prescribed by the physician. Institutions that have the capability to dispense temozolomide as daily doses in a blister pack may do so, taking specific precautions to ensure that the appropriate dose is provided and that the patient is educated to understand the daily dosing regimen.

For children unable to swallow the capsules whole, the oral capsules may be formulated into a suspension. To prepare a 10 mg/mL suspension triturate the contents of ten 100 mg capsules (1000 mg), 500 mg povidone K-30 and 25 mg anhydrous citric acid dissolved in 1.5 mL purified water in a glass mortar to form a uniform paste. To the paste add 50 mL of Ora-Plus® by adding a small amount, mixing, and then adding the balance. Transfer to a glass graduated cylinder. Add Ora-Sweet® or Ora-Sweet® SF to a total volume of 100 mL by rinsing the mortar with small amounts of the syrup (Ora-Sweet® or Ora-Sweet® SF). Rinse at least four times. Package in an amber plastic prescription bottle. The packaged suspension should be stored in the refrigerator at 2–8°C (36–46°F) for no more than 2 weeks after preparation. The suspension should be shaken well before each use. Procedures for proper handling and disposal of cytotoxic drugs should be used when preparing the suspension.

Extemporaneous temozolomide 10 mg/mL suspension can also be prepared using 100 mg temozolomide capsules mixed in Ora-Mix SF®. Open contents of the required number of 100 mg temozolomide capsules into a mortar and add Ora-Mix SF® until a paste forms. Add more vehicle until a liquid is formed (for each 100 mg capsule add 10 mL of Ora-Mix SF®). Transfer desired volume to a glass or polyethylene terephthalate bottle. Label the container, assigning a beyond-use-date of 30 days, for storage under refrigeration only.

Alternatively, the capsules can be opened and mixed with apple sauce or juice, which should be used immediately after mixing or must be used in 2 hours after mixing (refer to [Appendix V](#) in the protocol).

**Supplier:**

Commercially available. See package insert for further information.

**7.0 EVALUATIONS/MATERIAL AND DATA TO BE ACCESSIONED**

Timing of protocol therapy administration, response assessment studies, and surgical interventions are based on schedules derived from the experimental design or on established standards of care. Minor unavoidable departures (up to 72 hours) from protocol directed therapy and/or disease evaluations (and up to 1 week for surgery) for valid clinical, patient and family logistical, or facility, procedure and/or anesthesia scheduling issues are acceptable (except where explicitly prohibited within the protocol).

**7.1 Research Studies for which Patient Participation is Required**

**7.1.1 Rapid Central Pathology and Molecular Review**

Patients should be consented and enrolled on APEC14B1 followed by enrollment on the HGG Pre-Enrollment Eligibility Screening (Step 0) on the same day. See [Section 3.1](#) for complete details regarding Pre-Enrollment Eligibility Screening and [Section 3.1.1.4](#) for a list of required materials to be submitted on APEC14B1.

**7.2 Research Studies for which Patient Participation is Optional**

In consenting patients, correlative biology studies will be performed. See [Section 15.2](#) for complete details.

**7.3 End of Therapy & Follow-up**

STUDIES TO BE OBTAINED	End of Therapy	Every 3 months for Year 1 (i.e., 3, 6, 9, 12 months)	Every 4 months for Year 2 (i.e., 16, 20, 24 months)	Every 6 months for Year 3 (i.e., 30, 36 months)	Once yearly for Years 4–10
Physical Exam with VS	X				
Ht, Wt, BSA	X				
CBC, differential, platelets	X				
Creatinine, bilirubin	X				
AST/ALT	X				
Brain MRI	X	X	X	X	X
Tumor and biology samples (in consenting patients, see Section 15.2.2 )	X	X (at 6 and 12 months)	X (at 20 months)	X (at 30 months)	

The table above indicates required End of Therapy evaluations and required Follow-Up imaging scans. In addition, see COG Late Effects Guidelines for recommended post treatment follow-up: <http://www.survivorshipguidelines.org/>

**Note:** End of Therapy data should be submitted per the Case Report Forms (CRFs) schedule.

## 8.0 CRITERIA FOR REMOVAL FROM PROTOCOL THERAPY AND OFF STUDY CRITERIA

### 8.1 Criteria for Removal from Protocol Therapy

- a) Relapse or progressive disease (see [Section 10.4](#)).
- b) Refusal of further protocol therapy by patient/parent/guardian.
- c) Completion of planned therapy.
- d) Physician determines it is in patient's best interest.
- e) Unacceptable toxicity due to protocol therapy (see [Section 5.0](#)).
- f) Development of a second malignancy, including bone marrow findings consistent with acute myeloid leukemia (AML)/MDS. Note: Patients who develop MDS/AML on treatment should discontinue protocol therapy and be managed appropriately.
- g) Patient becomes pregnant.
- h) Patient starts breastfeeding.
- i) Repeat eligibility studies (if required) are outside the parameters required for eligibility (see [Section 3.3](#)).

Patients who are off protocol therapy are to be followed until they meet the criteria for Off Study (see below). Follow-up data will be required unless patient is taken off study.

### 8.2 Off Study Criteria

- a) Death.
- b) Lost to follow-up.
- c) Patient did not start radiation treatment within 31 days of definitive surgery (see [Section 3.3.5](#)).
- d) Patient did not start veliparib treatment within 34 days of definitive surgery (see [Section 4.1.1](#)).
- e) Patient enrollment onto another COG study with tumor therapeutic intent (e.g., at recurrence).
- f) Withdrawal of consent for any further data submission.
- g) The tenth anniversary of the date the patient was enrolled on this study.

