## 9.2 **Study Design**

This study will evaluate the efficacy of the planned regimen in two molecularly defined pediatric newly-diagnosed HGG subgroups. Stratum 1 will enroll patients who are wild-type with respect to H3 K27M, *BRAF*, and *IDH1/2*. Stratum 2 will enroll patients whose tumors are positive for *IDH1/2* mutation and wild-type for *BRAF* and H3 K27M. The primary efficacy endpoint is EFS in both strata and the efficacy of the regimen used in this study will be assessed by comparing the stratum-specific EFS outcome to clinically and molecularly matched historical controls. These historical controls have been derived from Korshunov et al., and from ACNS0822 for Stratum 1 and from Korshunov et al., ACNS0822, ACNS0423, the recent *Cell* meta-analysis paper, and the HERBY trial for Stratum 2. These historical data sets that will be used for these comparisons have already been extracted and will be stored in the COG file share for this study for ease of access at future analysis points. These data will not be updated as these cohorts are quite mature at the time of the design of this study.

[figure not shown]

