### 9.3 Methods of Analysis

For both strata, the primary analysis for EFS will be based on a 2-sample, 1 sided logrank test. For each stratum we will also consider Cox models that incorporate known prognostic factors as feasible including resection status (GTR vs. < GTR) and tumor grade (Grade 3 vs. 4), etc. to ensure that these variables do not have undue influence on the overall outcome. For patients with measurable disease at baseline, we will also report the objective response rate.

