**9.4 Evaluability for Toxicity and Efficacy Assessments**

All patients who start radiation therapy and receive at least 1 dose of veliparib will be evaluable for toxicity and efficacy assessments. The latter refers to the primary endpoint of EFS and secondary endpoints of objective response and OS.

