**9.5 Analysis Plan for Exploratory Objectives**

For the biology/molecular data, we will provide a frequency table summarizing the number of patients with each aberration/alteration detected in germline and/or tumor samples. For longitudinal plasma samples used to assess circulating tumor DNA, we will summarize the percentage of patients with samples as well as display/summarize any changes in molecular markers. When feasible we will explore the association of these aberrations with EFS/OS and objective response rates via Cox models and fisher exact tests, respectively. We will also explore associations between genetic variants and clinical/demographic variables including age, resection status, histology, etc. For analyses exploring associations of a large number of potential markers with clinical outcome, we will utilize false discovery rate approaches in order to control family-wise error rate.

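### Section 8.2(e) ends required follow-up when a relapsed patient joins another COG therapeutic study, so overall survival is informatively censored, probably upward in Stratum 2

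*Combined protocol and SAP*

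**What the plan says.** Section 8.2 lists the events that take a patient off study. Item (e) is "Patient enrollment onto another COG study with tumor therapeutic intent (e.g., at recurrence"). Item (g) otherwise sets the limit at the tenth anniversary of enrollment.

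Section 8.1 separates leaving protocol therapy from leaving the study. Progression ends protocol therapy but not follow-up. The section then adds: "Follow-up data will be required unless patient is taken off study".

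OS appears twice in the statistical section. Section 9.4 says of efficacy evaluability: "The latter refers to the primary endpoint of EFS and secondary endpoints of objective response and OS". Section 9.5 says of the molecular data: "When feasible we will explore the association of these aberrations with EFS/OS and objective response rates", with Cox models for the time-to-event outcomes.

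The primary endpoint is different. Section 9.2 states: "The primary efficacy endpoint is EFS in both strata". Section 9.3 states: "the primary analysis for EFS will be based on a 2-sample, 1 sided logrank test". Section 9.3 gives no method, censoring rule or sensitivity analysis for OS, and Section 1 lists no OS objective.

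**The concern.** Read together, 8.1 and 8.2(e) keep relapsed patients under survival follow-up for up to ten years, except those who enter another COG therapeutic study. Under the plan as written, those patients' last required survival record falls shortly after relapse.

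Kaplan–Meier and Cox analyses treat a censored patient as exchangeable with everyone still at risk at that time. Here the people still at risk include many who have not progressed. A group selected for having just relapsed is not exchangeable with them.

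Two things are at stake: the reported OS of a small, single-regimen cohort, and the marker associations with OS. With no concurrent control arm, follow-up that depends on relapse cannot cancel between arms. Deaths that were never recorded cannot be recovered in the analysis.

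**Working it through.** **1. The plan's own figures.** The documents give no OS figure to reproduce. The EFS design can be checked with var(log HR) = 1/d_hist + 1/d_new and power = Φ(|ln HR|/SE − z).

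- Stratum 2 (Section 9.2: 18 historical events, 13 new events, HR 0.45, one-sided 10%): SE = √(1/18 + 1/13) = 0.364; 0.799/0.364 = 2.19; Φ(2.19 − 1.28) = 81.9%, against a stated 80%.
- Stratum 1 (91 and 35 events, HR 0.55, one-sided 5%): SE = √(1/91 + 1/35) = 0.199; 0.598/0.199 = 3.01; Φ(3.01 − 1.645) = 91.3%, against a stated 90%.

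The EFS design reproduces. Recurrence is already an EFS event, so leaving the study at or after recurrence changes neither these event counts nor the power.

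**2. Direction of the OS bias.** At a given time, let U be the share of patients unprogressed, R_n the share relapsed who did not join another COG study, and R_j the share relapsed who did. Let μ be the death hazard of relapsed non-joiners and φμ that of joiners. Ignoring deaths before progression and the short gap between relapse and joining:

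- true hazard = μ(R_n + φR_j)/(U + R_n + R_j)
- hazard seen after censoring = μR_n/(U + R_n)

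The seen hazard is too low, and OS too high, whenever φ > R_n/(U + R_n). With equal prognosis (φ = 1) the bias is always upward. It reverses only if joiners die at less than the average rate of everyone who remains at risk.

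An illustration at 3 years, with historical PFS, 12-month median survival after progression and 10% joining:

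- Stratum 2: PFS = 0.611 × (0.358/0.611)^(1/3) = 0.511 and OS = 0.695, so relapsed and alive = 0.184. R_n = 0.9 × 0.184 = 0.166. Threshold = 0.166/(0.511 + 0.166) = 0.25.
- Stratum 1: PFS = 0.222 × (0.125/0.222)^(1/3) = 0.183 and OS = 0.379, so relapsed and alive = 0.196. R_n = 0.176. Threshold = 0.176/(0.183 + 0.176) = 0.49.

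In Stratum 2 joiners would need about a quarter of the non-joiners' hazard for the sign to change. In Stratum 1 about a half is enough.

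**3. Size.**

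- From Section 9.2: Stratum 2 control PFS of 85.4%, 61.1% and 35.8% at 1, 2 and 5 years, taken as piecewise exponential.
- Assumed, because the documents do not give them: exponential survival after progression with median 12 or 24 months; 10–50% of relapsing patients joining another COG study; censoring one month after relapse.

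Results from 400,000 simulated patients per scenario, with joiners' prognosis equal to that of other relapsed patients:

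| Median survival after progression | Time | True OS | Bias, 10% join | OS read, 20% join | OS read, 50% join |
|---|---|---|---|---|---|
| 12 months | 3 years | 69.5% | +1.9 points | 73.3% | 80.2% |
| 12 months | 5 years | 48.3% | +2.6 points | 53.8% | 64.6% |
| 24 months | 3 years | 80.0% | +1.3 points | 82.6% | 87.2% |
| 24 months | 5 years | 61.1% | +2.0 points | 65.3% | 73.5% |

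At 3 years the 20–50% range is therefore +2.6 (82.6 − 80.0) to +10.7 points (80.2 − 69.5).

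**4. Sensitivity of the 3-year bias.**

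- Design effect (HR 0.45), 10–50% joining, median 1–2 years, equal prognosis: +0.7 to +6.3 points in Stratum 2.
- Joiners with half the hazard, control PFS, 12-month median, 20–50% joining: +2.0 to +6.1 points in Stratum 2.
- Joiners with half the hazard, 10–50% joining, median 0.5–2 years: +0.4 to +9.8 points in Stratum 2 and −0.5 to +10.0 in Stratum 1.
- Joiners with a quarter of the hazard, same ranges: −0.1 to +5.2 points in Stratum 2 and −4.6 to +1.4 in Stratum 1.

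**The case against.** A reader might infer that OS will be overstated. The documents do not support that. The direction depends on how fit the joiners are relative to other relapsed patients, and trial entrants may well be selected for fitness. The share joining and the survival after progression are also absent from the protocol. Only COG studies trigger 8.2(e): patients who relapse onto other trials, or are treated off trial, stay in follow-up. These points stand, and they are why the size is given as a range and the direction as probable, for Stratum 2 only.

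A reader might also infer that the trial's conclusion is at risk, or that a planned OS comparison would favor the regimen. Neither follows. The historical comparison is on EFS, and no OS comparison is specified. The documents do not say whether the historical cohorts used a similar off-study rule. They also give no evidence that access to relapse studies depends on genotype, so distorted marker associations are a possibility only.

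The bias may be small beside sampling error. In Stratum 2, 20–50% of 13 expected events is about 3 to 6 patients, and the binomial standard error of a 69.5% OS in 30 patients is √(0.695 × 0.305/30) = 8.4 points. That is fair for a single estimate, but it does not justify an avoidable bias.

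Finally, 8.1 says only that follow-up is not required after the patient is off study, so censoring is inferred. Every patient is already on the COG registry protocol, which includes outcome (Section 3.1), and keeps one COG patient ID (Section 3.2.1). A route to the data therefore exists. No section connects it to OS, so it makes the fix cheap without removing the gap.

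**Conclusion.** The point holds in a limited form. Sections 8.1 and 8.2(e) together stop required follow-up for patients selected by a recent relapse, and OS is a named secondary endpoint with no rule that covers this exit. OS and the exploratory OS associations are subject to informative censoring, probably upward in Stratum 2.

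The size cannot be derived from the documents. With control-like PFS, median survival after progression of 1–2 years and joiners of equal prognosis, 3-year OS is overstated by about 1–2 points at a 10% share and about 3–11 points at 20–50%. It is less under the design HR, and near zero or slightly negative if joiners have about a quarter of the death hazard. In Stratum 1, which is closed to accrual, the sign can change from about a half.

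The primary EFS test, its power and its futility monitoring are unaffected by enrollment at or after recurrence. This is a low-cost improvement to a secondary endpoint, not a threat to the primary result.

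**What to change.** Reword 8.2(e) so that joining another COG therapeutic study ends study-specific evaluations only. Vital status, with date of death or last contact, should continue to be collected to the tenth anniversary, subject to withdrawal of consent under 8.2(f). The source can be the second COG study's record or the COG registry on which every patient is already enrolled. Adjust the follow-up sentence in 8.1 to match, and state in 9.3 or 9.4 that OS is not censored at that enrollment.

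If the link cannot be made for some patients, state the OS censoring rule, report how many left under 8.2(e) and when, and add a sensitivity analysis over a range of death hazards for them after they leave.

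The cost is a small data-linkage task within one cooperative group and possibly a change to consent wording. No visits are added, and treatment and the EFS analysis do not change. With complete vital status, the bias from this source is zero.
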